3.2 Study Population

Patients admitted into Hospital Selayang from

- 1st July 2001 to 30th June 2002
- 1st July 2006 to 30th June 2007
- 1st July 2011 to 30th June 2012
- 1st July 2016 to 30th June 2017

3.3 Inclusion Criteria

- a) Age of 18 and above at time of hospital admission
- b) HA-AKI is defined by any patient who developed AKI (as per definition below) after 48 hours of hospital admission.
- c) Definition of AKI(9):

- i. An increase in serum creatinine of 0.3 mg/dl (26.5 μ mol/l) within 48 hours *OR*
- ii. An increase in serum creatinine to more or equal to 1.5 times baseline, which is known or presumed to have occurred within the prior 7 days

d) Definition for baseline creatinine(9):

- i. The baseline creatinine level is defined as the creatinine level at or within 7 days before the hospital admission, *OR*
 - ii. at the hospital admission *OR*
 - iii. the lowest creatinine (excluding the post dialysis creatinine if dialysis is initiated) during the index hospitalisation for those whose baseline creatinine were unknown.

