2.2 *Specific Objectives:*

- To determine the incidence pattern of Hospital-acquired Acute Kidney Injury in Hospital Selayang
- To study the determinants associated with development of Hospital-acquired Acute Kidney Injury in Hospital Selayang

- To describe the survival outcome pattern of admissions with Hospital-acquired Acute Kidney Injury, admissions with Community-acquired Acute Kidney Injury and admissions without Acute Kidney Injury in Hospital Selayang

3. Methodology

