3.1 Study Type and Design

This is a retrospective cohort study involving 5-yearly trend from 2002 to 2017 for analysis. Laboratory serum creatinine (SCr) results of all patients admitted during study period will be retrieved from the hospital Laboratory Information System. A preliminary screening list will be generated by using STATA program from the SCr results. The nephrologist will then determine HA-AKI as per inclusion and exclusion criteria. Data collectors will collect all relevant data from these patients.

[figure not shown]

Figure 1. Flow chart of the study

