3.4 Exclusion Criteria

- End Stage Renal Failure and on Renal Replacement Therapy (HD, PD or Renal Transplant)

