3.6 Study Outcomes

1. Incidence of Hospital-acquired AKI at our centre during study period
2. Renal recovery at 90 days after AKI diagnosis
Definition for renal recovery:
 - a. Full recovery: Return of serum creatinine to or below baseline or within 20% of baseline creatinine
 - b. Partial recovery: Serum creatinine remaining 20% above the baseline, but below 50% of the baseline and not dialysis dependent or if previously requiring dialysis and now is dialysis Independent.
 - c. Failure to recover: Serum creatinine remains 50% above the baseline or dialysis dependent.
3. In-hospital mortality (from date of AKI diagnosis until date of death in hospital)

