3.7 Sample Size

The primary outcome of interest is development of HA-AKI during admission at our centre. The incidence of Hospital-acquired AKI at our centre at March 2017 was 1.19% based on one ongoing study (A prospective, multicenter, observational study to determine the incidence and outcome of Acute Kidney Injury among hospitalised patients in Malaysia). The nine variables to be investigated for predictors of HA-AKI are age, gender, ICU

admission, race, nephrotoxin use, diabetes mellitus, hypertension, congestive heart failure and chronic obstructive pulmonary disease. With an estimation of 15 events per predictor, a minimum of 135 events would be needed, translating to a minimal of 11345 patients at our centre required for the study. The study population fits the minimum sample size requirement as 170283 adult admissions were recorded in total (22788 for Year 2002, 41731 for Year 2007, 46330 for Year 2012 and 59434 for Year 2017).

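### No at-risk set is stated for the HA-AKI regression or incidence: the only visible cohort includes short stays and community-acquired AKI, neither of which can become a case

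*Combined protocol and SAP*

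**What the plan says.** All references are to the combined protocol and SAP.

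- **Case definition, 3.3(b):** "HA-AKI is defined by any patient who developed AKI (as per definition below) after 48 hours of hospital admission".
- **Population, 3.2 to 3.4:** admissions in four one-year windows, aged 18 or over. The one exclusion is "End Stage Renal Failure and on Renal Replacement Therapy (HD, PD or Renal Transplant".
- **Count, 3.7:** "The study population fits the minimum sample size requirement as 170283 adult admissions were recorded in total". The section does not say whether the 3.4 exclusion was applied to this count.
- **Incidence, 3.6:** outcome 1 is "Incidence of Hospital-acquired AKI at our centre during study period", with no denominator.
- **Regression, 3.10:** multiple logistic regression of outcome on risk factors, with no analysis set and no definition of the non-cases. The nine predictors in 3.7 are age, gender and ICU "admission, race, nephrotoxin use, diabetes mellitus, hypertension, congestive heart failure and chronic obstructive pulmonary disease".
- **Groups, 2.2:** the survival objective separates HA-AKI from "admissions with Community-acquired Acute Kidney Injury and admissions without Acute Kidney Injury in Hospital Selayang". Section 3.10 does not say how community-acquired AKI (CA-AKI) is handled in the HA-AKI regression.
- **Data collection, 3.1:** directly after the nephrologist determines HA-AKI, "Data collectors will collect all relevant data from these patients". It is unclear whether this includes non-cases.

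**The concern.** A patient discharged or dead by 48 hours cannot meet 3.3(b). In a regression on all admissions, that patient is a non-case by construction, whatever the risk to the kidney. A predictor more common among patients who stay beyond 48 hours will then be associated with HA-AKI even if it has no effect on it, and one more common in short stays will look protective. CA-AKI admissions left among the non-cases add a second distortion: a predictor common in CA-AKI is pushed towards looking protective.

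HA-AKI is the primary outcome of interest (3.7), its determinants are the second objective, and section 1 says the findings are meant to guide prevention. A predictor of length of stay taken for a predictor of kidney injury would carry through to that use.

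For incidence the stake is smaller. A per-admission rate and a rate among stays at risk answer different questions, and 3.6 does not say which is meant.

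**Working it through.** **1. The plan's own figures.** Events needed: 9 predictors × 15 = 135. Admissions: 135 / 0.0119 = 11,344.5, so 11,345, as stated. The four years: 22,788 + 41,731 + 46,330 + 59,434 = 170,283, as stated. Expected events at 1.19%: 170,283 × 0.0119 = 2,026. The arithmetic in 3.7 is correct.

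**2. Is the event count at risk?** If the 1.19% applies only to at-risk stays, an at-risk share of 50% gives 2,026 × 0.5 = 1,013 events, and 40% gives about 811. The minimum is missed only if the share falls below 135 / 2,026 = 6.7%.

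**3. Odds ratio of a null predictor if all admissions are used.** Every share and prevalence here is an assumption. Let q be the share of stays of 48 hours or less without AKI, c the share with CA-AKI, and a = 1 − q − c the share at risk. The risk among those at risk is r = 0.0119 / a, the same for exposed and unexposed. Predictor prevalence is 40% in the at-risk stays, pS in the short stays and 60% in CA-AKI.

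- Cases: exposed 0.4·a·r = 0.00476; unexposed 0.6·a·r = 0.00714.
- Non-cases: exposed 0.4·a·(1 − r) + q·pS + 0.6·c; unexposed 0.6·a·(1 − r) + q·(1 − pS) + 0.4·c.

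Example with q = 0.3, pS = 0.3, c = 0: the non-case shares are 0.36524 and 0.62286, so OR = (0.00476 × 0.62286) / (0.00714 × 0.36524) = 1.14.

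| q | pS | c = 0 | c = 3% | c = 5% | c = 10% |
|---|---|---|---|---|---|
| 0.3 | 0.3 | 1.14 | 1.11 | 1.09 | 1.04 |
| 0.5 | 0.2 | 1.56 | 1.52 | 1.49 | 1.42 |
| 0.3 | 0.4 (equal) | 1.00 | 0.98 | 0.96 | 0.92 |
| 0.3 | 0.5 | 0.88 | – | – | 0.81 |
| 0.5 | 0.6 | 0.66 | – | – | 0.61 |

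With short stays alone (c = 0) the range is 0.66 to 1.56. CA-AKI at the assumed 60% prevalence lowers every value.

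With 2,026 events, the first row has p = 0.005, 0.025, 0.06 and 0.35 from left to right, and every p in the second row is below 0.001. With only 135 events, the first row has p of 0.47 or more, and the second row runs from 0.011 to 0.046.

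**4. Does adjustment help?** A logistic model was fitted to expected cell counts with c = 0 and one covariate of 40% prevalence. Predictor prevalence by covariate was 25% v 55% (first row) or 14% v 54% (second row), calibrated to the same crude odds ratio.

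| Covariate OR for a stay over 48 hours | 1 | 1.65 | 2.72 | 4.48 |
|---|---|---|---|---|
| First row, adjusted OR | 1.14 | 1.09 | 1.04 | 1.01 |
| Second row, adjusted OR | 1.56 | 1.40 | 1.26 | 1.15 |

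In these settings adjustment nearly removes the small distortion and reduces the larger one. Adjustment and CA-AKI were not combined.

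**5. Level and trend of the incidence.** If the 1.19% is per admission (its denominator is not stated), removing short stays gives 1.19 / 0.70 = 1.70% to 1.19 / 0.50 = 2.38%. Removing 3% to 10% CA-AKI as well gives 1.19 / 0.67 = 1.78% to 1.19 / 0.40 = 2.98%. For the trend at constant risk, the ratio of per-admission rates equals the ratio of at-risk shares: 1.00 if the share is stable, 55 / 65 = 0.85 if it falls from 65% to 55%, and 1.18 for the reverse.

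**The case against.** **Figure 1.** The flow chart in 3.1 is not visible and could contain a stay-length or CA-AKI step. This stands. The point is limited to the visible text, and if the figure has the step, 3.6 and 3.10 need only repeat it.

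**The plan never says it will regress on all 170,283 admissions.** This is correct. Section 3.7 uses the count to show that the sample is large enough, and 2.2 names CA-AKI as a separate group, so the analysts may intend to set it aside. A reader might infer that the plan commits itself to the wrong set. The documents support only that no narrower set is stated and that the stated limits admit stays that cannot be cases.

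**The per-admission rate is legitimate.** This also stands. A reader might infer that the planned incidence is wrong, or that the four-period comparison will be spurious. Neither follows: the rate is a coherent measure of burden, and the trend shifts only if the at-risk share changed between periods, which nothing in the documents shows.

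**The size is assumed.** This stands too. The odds ratios fall on both sides of 1.00, and the outer cases have no support in the documents. A known bias, or a known direction, cannot be claimed.

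**Length of stay is not a predictor in 3.7.** A reader might infer that it should be added. Section 1 lists length of hospitalisation among the outcomes linked with HA-AKI, so adjusting for it could itself introduce bias. Its absence is not a defect.

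**Conclusion.** The concern holds in a limited form and should be fixed. The visible text gives the regression no cohort narrower than adult admissions without end-stage renal failure or renal replacement therapy. Under 3.3(b) that cohort includes short stays, which cannot be cases, and CA-AKI, which counts among the non-cases unless set aside. Used as it stands, it can give a predictor with no effect on HA-AKI an odds ratio away from 1.

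How far and in which direction is unknown. The crude range of 0.66 to 1.56 for short stays alone rests wholly on assumed shares and prevalences, includes 1.00, and may shrink with adjustment. For incidence, the fault is only an unstated denominator. A reader might also infer that the study is too small; at any at-risk share above 6.7% it is not. Confidence is medium, because Figure 1 cannot be seen.

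**What to change.** - **3.10:** restrict the HA-AKI logistic regression to adult admissions without end-stage renal failure or renal replacement therapy, with a stay over 48 hours, and not classified as CA-AKI (AKI by 48 hours). Use the same classification as for objective 3.
- **3.6:** state the incidence denominator. By period, report the per-admission rate, the rate in the at-risk set, and the share of stays over 48 hours.
- **3.1:** make clear that predictor data cover the non-cases in the regression.
- **Figure 1:** if it already contains the restriction, repeat it in 3.6 and 3.10.

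Optional: repeat the incidence among stays with at least two creatinine values, one of them after 48 hours, as a sensitivity analysis. That subset is itself selected by testing. Moving 3.3(b) to (d) into the outcome section is editorial.

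**Cost.** The sampling design does not change, but the work is more than wording. Admission and discharge times and AKI timing must be derived for all analysed stays. The CA-AKI classification is already needed for objective 3. Covariates, including nephrotoxin use, must be obtained for non-cases, which the regression needs in any case; 3.8 allots five months to data collection and analysis.

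**What remains.** Section 3.3(d)(iii) takes the lowest value "during the index hospitalisation for those whose baseline creatinine were unknown", so AKI status at 48 hours can depend on later creatinine results. Unequal time at risk and unequal testing after 48 hours are not removed. The at-risk rate may not be comparable with the 1.19% planning figure, whose denominator is not stated.

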3.10 Statistical Analysis Plan

The analyses will be performed using IBM SPSS Statistics for Windows (Version 23.0. Armonk, NY: IBM Corp.). Descriptive statistics will be utilized for selected variables. The results will be presented as frequencies and percentage for Categorical Data. Numerical Data which is normally distributed will be presented as mean and standard deviation while median and interquartile range will be presented for Numerical Data which is not normally distributed.

Comparing Numerical Data which is normally distributed between two groups will be analysed using the Independent t-test while Mann-Whitney test will be used if not normally distributed. Multiple logistic regression will be used to study association between risk factors (Numerical Data/Categorical Data) and outcome (Categorical Data). The survival analyses and survival curves from the date of diagnosis until death will be performed using the Kaplan-Meier method, to estimate the index hospitalisation survival rate. All probability values will be two-sided and a level of significance of less than 0.05 (p-value < 0.05) will be considered as statistically significant.

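### For unknown-baseline patients first tested at their peak, d(iii) makes a later in-stay low both the route to HA-AKI under c(ii) and the yardstick for 90-day recovery

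*Combined protocol and SAP*

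**What the plan says.** Section 3.3 dates HA-AKI by timing: "HA-AKI is defined by any patient who developed AKI (as per definition below) after 48 hours of hospital admission". AKI is met in either of two ways. Criterion c(i) is "An increase in serum creatinine of 0.3 mg/dl" (26.5 µmol/l) within 48 hours and needs no baseline. Criterion c(ii) is "An increase in serum creatinine to more or equal to 1.5 times baseline, which is known or presumed to have occurred within the prior 7" (the unit being days).

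Baseline is "the creatinine level at or within 7 days before the hospital admission" under d(i), or the value at admission under d(ii). Where neither is known, d(iii) uses "the lowest creatinine (excluding the post dialysis creatinine if dialysis is initiated) during the index hospitalisation for those whose baseline creatinine were unknown".

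Section 3.6 judges recovery at 90 days against the same baseline. Full recovery is "Return of serum creatinine to or below baseline or within 20% of baseline creatinine". The third outcome is "In-hospital mortality (from date of AKI diagnosis until date of death in hospital"), and section 3.10 adds: "The survival analyses and survival curves from the date of diagnosis until death will be performed using the Kaplan-Meier method".

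Section 3.1 describes a program screen of creatinine results, followed by a nephrologist's decision under the same criteria. The plan gives no rule on when a d(iii) sample must be drawn, no definition of the diagnosis date, no landmark or delayed entry, and no sensitivity analysis on baseline.

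**The concern.** A baseline should describe the patient before the injury. Under d(iii) it may be drawn afterwards, at the best point of the recovery. For a patient whose first value is the peak, case status under c(ii) then depends on surviving, and improving, long enough for a low value to be recorded. Those are close to the outcomes that the study sets out to describe.

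Two results are exposed. For 90-day recovery, a patient recognised this way is compared with his or her own recovered value. For survival, patients who die without the required fall drop out of HA-AKI and into the no-AKI group of the third specific objective (section 2.2), while those recognised must have lived from the high value to the low one.

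**Working it through.** **1. The plan's own figure.** Section 3.7: 9 predictors × 15 events = 135; 135/0.0119 = 11,344.5, rounded up to 11,345. This reproduces. At 1.19%, the 170,283 admissions would give about 2,026 HA-AKI admissions. The documents do not say how many fall under d(iii).

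**2. The fall that c(ii) requires.** Let the first value P be the peak and L the lowest later non-dialysis value. P/L ≥ 1.5 means L ≤ P/1.5, a fall of at least 1 − 1/1.5 = 33.3%. For P = 240 µmol/l, L must be 160 or lower.

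**3. The rules applied to constructed series.** All are in µmol/l, first tested at 72 hours, with no earlier value.

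| Series | Lowest | c(i) | c(ii) | Recognised |
|---|---|---|---|---|
| 240, 245, 238 | 238 | no (+5) | 245/238 = 1.03 | no |
| 240, 210, 180 | 180 | no | 240/180 = 1.33 | no |
| 300 only | 300 | no | 1.00 | no |
| 400, then post-dialysis falls only | 400 | no | 1.00 | no |
| 240, 190, 150 | 150 | no | 240/150 = 1.60 | yes, by fall |
| 240, 200, 140, 100 | 100 | no | 240/100 = 2.40 | yes, by fall |
| 240, 275, 300 | 240 | yes (+35 in 24 h) | 300/240 = 1.25 | yes, by rise |
| 240, 300, 370 | 240 | yes (+60 in 48 h) | 370/240 = 1.54 | yes, by rise |

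In both fall-recognised series the last value is the baseline itself (ratio 1.00).

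**4. Recovery.** Take 240, 190, 150 and assume an unmeasured usual level of 80. The full-recovery limit is 1.2 × 150 = 180 under d(iii) and 1.2 × 80 = 96 against the usual level. A day-90 value of 150 is full recovery under the rule (150/150 = 1.00) and failure against the usual level (150/80 = 1.88).

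Now let the day-90 value vary log-normally around the in-hospital low with log SD s. The chance of full recovery under the rule is Φ(ln 1.2/s), with ln 1.2 = 0.182:
- s = 0.1: Φ(1.82) = 97%
- s = 0.2: Φ(0.91) = 82%
- s = 0.3: Φ(0.61) = 73%

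The patient's usual level does not enter this formula. A simulation of fall-recognised cases gives 30%, 33% and 36% against the usual level. Its assumptions are a median usual level of 80 with log SD 0.25, a first value of 1.5 plus an exponential of mean 0.8 times that level, and survivors resolving on average 65% of the excess. The comparator moves with the assumed distribution of resolution, and the set-up never lets the low fall below the usual level.

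**5. Mortality.** Let m be true mortality, and let f and r be the shares recognised by a fall and by a further rise in those who die (d) and those who survive (s). Mortality among recognised cases is

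m(f_d + r_d) / [m(f_d + r_d) + (1 − m)(f_s + r_s)].

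All shares below are assumptions.

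| f_d, f_s | r_d, r_s | m = 20% | m = 40% |
|---|---|---|---|
| 0.10, 0.70 | 0, 0 | 0.02/(0.02 + 0.56) = 3.4% | 8.7% |
| 0.10, 0.70 | 0.30, 0.10 | 0.08/(0.08 + 0.64) = 11.1% | 25.0% |
| 0.10, 0.70 | 0.60, 0.10 | 0.14/(0.14 + 0.64) = 17.9% | 36.8% |
| 0.05, 0.60 | 0.80, 0.20 | 0.17/(0.17 + 0.64) = 21.0% | 41.5% |

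The first row, recognition by fall only, is well below the truth. Once enough worsening patients enter by a further rise, the shortfall disappears or slightly reverses.

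**6. Time origin.** If diagnosis is dated at the raised value, a fall-recognised case cannot die before the low value is drawn, so that interval is immortal time. If diagnosis is dated when the criterion is met, it is not. The plan does not say which date applies.

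**The case against.** The strongest reply is that the rule does not work through falls alone. Criterion c(i) needs no baseline, and c(ii) can be met by a rise from the first value; the last two series in the table qualify without ever falling. A reader might infer that d(iii) recognises a case only if creatinine later falls. The text does not support that, and the point is limited to patients whose first value is at or near the peak.

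A reader might also infer that recovery becomes 100% and mortality 0% by construction. Neither follows. Creatinine can rise again by day 90, death after the low value is possible, and a low below the patient's usual level makes full recovery harder to reach. Nor can it be said that HA-AKI mortality is understated overall: step 5 shows that the net direction depends on how many patients are recognised by a rise. That the bias differs between the four windows is possible, but nothing in the documents shows it.

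Scope is uncertain too. If the first test of the stay is read as the admission value, d(ii) applies and d(iii) rarely does. Against that, d(i) reaches back only 7 days, so patients with older values count as unknown. A first raised value after 48 hours also does not prove onset after 48 hours, so HA-AKI status is not automatic.

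These replies narrow the point but do not remove it. The nephrologist applies the same criteria, so that step does not break the link between the later low value, case status and the recovery reference.

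**Conclusion.** The point holds in limited form. For an unknown-baseline patient whose first value is at or near its peak and does not rise further, c(ii) with d(iii) requires a non-dialysis fall of at least one third in the same stay. Patients without it are counted as no AKI. Fall-recognised cases have met the full-recovery limit in hospital against their own low, so 90-day recovery tends to be overstated. That direction rests on in-hospital resolution usually being incomplete. Mortality is selected downward among these cases, with immortal time added if diagnosis is dated at the raised value.

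Over all unknown-baseline patients the direction for mortality is not fixed. Neither the size of the subgroup nor the bias can be computed from the documents; the percentages in steps 4 and 5 are illustrations under assumed inputs. The change is still worth making before analysis, because the problem can be identified from sample dates and the recovery result could otherwise mislead if the subgroup is large.

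**What to change.** In 3.6 and 3.10, flag each HA-AKI case by whether its baseline sample was drawn before the qualifying raised value (d(i), d(ii), or an earlier d(iii) value) or on or after it. Then:

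- Base the main analysis of 90-day recovery on cases with a baseline drawn before onset.
- Base the main analysis of in-hospital mortality and the Kaplan-Meier curves on those cases plus cases that qualify by a c(i) rise.
- Report the cases with a post-onset baseline separately for each window. This also shows how large the group is.
- Give the all-cases result as a sensitivity analysis, stating which date is taken as diagnosis.

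The cost is a few lines of text and one derived flag from the creatinine extract that section 3.1 already retrieves. The main recovery and survival estimates will use somewhat fewer cases.

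Two limits remain. The flag does not recover patients missed for want of a fall; a separate group of raised values that never fall cannot be defined without a baseline and could take in stable chronic kidney disease. It also cannot detect a first value that was already raised before a further rise.
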